6.7. Methodology for Noninferiority Test

For assessing noninferiority of ixekizumab to adalimumab, missing data will be imputed using the NRI method. Noninferiority analysis will be performed on the ITT population using a prespecified fixed margin approach. There is no universally accepted value for what is considered to be a clinically unimportant difference between 2 treatments for a particular efficacy measure. We will consider the points from EMEA Committee for Medicinal Products for Human Use (CHMP) (CHMP 2005) and FDA guidance (2016) which state that an appropriate noninferiority margin should be based on both clinical and statistical grounds.

The null hypothesis will be rejected if the lower bound of the 2-sided 95% CI for the difference in proportions of responders on ixekizumab minus adalimumab is greater than the prespecified margin, meaning ixekizumab will be deemed noninferior to adalimumab. If the lower bound of the CI exceeds 0 (the corresponding p-value from the logistic regression model will also be produced), and ixekizumab will be deemed superior to adalimumab based on the p-value. The 95% CIs for the difference in proportions will be calculated using the simple asymptotic method, without continuity correction (that is, normal approximation to the binomial distribution).

Based on EMEA CHMP (CHMP [WWW]), FDA guidance (FDA [WWW]), and Weinblatt et al. (2013), a noninferiority margin of -12.0% for ACR50 between ixekizumab and adalimumab (ie, response rate of ixekizumab – response rate of adalimumab) is considered appropriate. This noninferiority margin represents an approximately 50% preservation of the adalimumab treatment effect (based on the difference between adalimumab and placebo) observed in a historical Phase 3 study for adalimumab 40 mg twice weekly compared with placebo (Mease et al. 2005) and Study RHAP (Mease et al. 2016).

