10.3.1.3. Adjustment for Multiple Comparisons

A multiple testing strategy for the primary and major secondary endpoints will be implemented to control the family-wise type I error rate at a 2-sided α level of 0.05. The primary and major secondary endpoints will be sequentially tested in the following order to compare ixekizumab vs adalimumab, using the primary analysis method.

- 1. Test 1 for Primary Endpoint Proportion of patients simultaneously achieving ACR50 and PASI 100 at Week 24: A superiority test of the primary endpoint will be performed at an overall 2-sided $\alpha = 0.05$ using the methods described in Section 10.3.3.1.1.
- 2. Test 2 for Major Secondary Endpoint #1 Proportion of patients achieving ACR50 at Week 24: If the test for the primary endpoint is significant, then a noninferiority test for the major secondary endpoint #1 will be performed using the methods described in Section 10.3.3.3.
- 3. Test 3 for Major Secondary Endpoint #2 Proportion of patients achieving PASI 100 at Week 24: If the test for major secondary endpoint #1 is significant, then a superiority test for major secondary endpoint #2 will be performed using the methods described in Section 10.3.3.1.1.

If a test in this sequence is not significant, all subsequent tests will be considered nonsignificant.

There will be no adjustment for multiple comparisons for any other analyses.

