10.3.3.3. Methodology for Noninferiority Test

For assessing noninferiority of ixekizumab to adalimumab, missing data will be imputed using the NRI method. Noninferiority analysis will be performed on the ITT population using a prespecified fixed margin approach. There is no universally accepted value for what is considered to be a clinically unimportant difference between 2 treatments for a particular efficacy measure. We will consider the points from EMEA Committee for Medicinal Products for Human Use (CHMP) (CHMP 2005) and FDA guidance (2016) which state that an appropriate noninferiority margin should be based on both clinical and statistical grounds.

The null hypothesis will be rejected if the lower bound of the 2-sided 95% CI for the difference in proportions of responders on ixekizumab minus adalimumab is greater than the prespecified margin, meaning ixekizumab will be deemed noninferior to adalimumab. If the lower bound of the CI exceeds 0 (the corresponding p-value will also be produced), then ixekizumab will be deemed superior to adalimumab. The 95% CIs for the difference in proportions will be calculated using the simple asymptotic method, without continuity correction (that is, normal approximation to the binomial distribution).

Based on EMEA CHMP (CHMP 2005), FDA guidance (2016), and Weinblatt et al. (2013), a noninferiority margin of –12.0% for ACR50 between ixekizumab and adalimumab (ie, response rate of ixekizumab – response rate of adalimumab) is considered appropriate. This noninferiority margin represents an approximately 50% preservation of the adalimumab treatment effect (based on the difference between adalimumab and placebo) observed in a historical Phase 3 study for adalimumab 40 mg twice weekly compared with placebo (Mease et al 2005) and Study RHAP.

If it is deemed appropriate to perform noninferiority tests on endpoints other than ACR50, the details about selection of noninferiority margins for the other endpoints will be presented in the SAP.

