6.6. Multiple Comparisons/Multiplicity

A multiple testing procedure for the primary and major secondary endpoints will be implemented to control the family-wise type I error rate at a 2-sided α level of 0.05. The primary and major secondary endpoints will be sequentially tested in the following order to compare ixekizumab versus adalimumab, using the primary analysis method.

1. Test 1 for Primary Endpoint – Proportion of patients simultaneously achieving ACR50 and PASI 100 at Week 24: A superiority test of the primary endpoint will be performed at an overall 2-sided $\alpha = 0.05$ using the methods described in Section 6.2.1.
2. Test 2 for Major Secondary Endpoint #1 – Proportion of patients achieving ACR50 at Week 24: If the test for the primary endpoint is significant, then a noninferiority test for the major secondary endpoint #1 will be performed using the methods described in Section 6.7.
3. Test 3 for Major Secondary Endpoint #2 – Proportion of patients achieving PASI 100 at Week 24: If the test for major secondary endpoint #1 is significant, then a superiority test for major secondary endpoint #2 will be performed using the methods described in Section 6.2.1.

If a test in this sequence is not significant, all subsequent tests will be considered nonsignificant.

There will be no adjustment for multiple comparisons for any other analyses.

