6.12.1.2. Methodology for Major Secondary Outcomes

The major secondary endpoints are as follows:

1. Proportion of patients achieving ACR50 in each treatment group at Week 24
2. Proportion of patients achieving PASI 100 in each treatment group at Week 24

The analyses of the secondary endpoints will be based on the ITT population in the Open-Label Treatment Period (Period 2) comparing ixekizumab versus adalimumab at Week 24 using methods described in Section [6.7](#) for the major secondary endpoint #1 and using methods from Section [6.2.1](#) for the major secondary endpoint #2. Missing data will be imputed using the NRI method described in Section [6.4.1](#).

A multiple testing procedure, as described in Section [6.6](#), will be used for testing the primary and major secondary endpoints.

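### SAP 6.7 allows an ACR50 superiority claim that is not a step in the SAP 6.6 test sequence, so the claim lies outside the 5% family-wise control (minor; a text change settles it)

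*SAP*

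**What the plan says.** SAP 6.6 makes the control claim: "A multiple testing procedure for the primary and major secondary endpoints will be implemented to control the family-wise type I error rate", at a 2-sided level of 0.05. It then lists three steps.

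- Test 1 is superiority on the composite of ACR50 and PASI 100.
- Test 2 is ACR50: if Test 1 succeeds, "then a noninferiority test for the major secondary endpoint #1 will be performed using the methods described in Section 6.7".
- Test 3 is PASI 100: "If the test for major secondary endpoint #1 is significant, then a superiority test for major secondary endpoint #2 will be performed".

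The section closes with "There will be no adjustment for multiple comparisons for any other analyses". Protocol 10.3.1.3 has the same three steps and the same closing line; its Test 2 reads "If the test for the primary endpoint is significant, then a noninferiority test for the major secondary endpoint #1 will be performed".

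The section that Test 2 points to contains a second ACR50 decision. Protocol 10.3.3.3 states it plainly: "If the lower bound of the CI exceeds 0 (the corresponding p-value will also be produced), then ixekizumab will be deemed superior to adalimumab". SAP 6.7 keeps the rule, names the logistic regression p-value and ends "and ixekizumab will be deemed superior to adalimumab based on the p-value".

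Two other places bear on the status of that decision. SAP 6.12.1.2 says that the multiple testing procedure "will be used for testing the primary and major secondary endpoints", and ACR50 is one of the latter. SAP Table RHCF.6.4 labels the logistic comparison of ACR50 at Week 24 a major secondary analysis, although the ACR50 test in the sequence is a noninferiority test on a confidence interval. Against this, the ACR50 objective in SAP Table RHCF.4.1 is noninferiority only.

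**The concern.** The plan provides for four possible declarations on the primary and major secondary endpoints but orders only three. One reader could take an ACR50 superiority result as confirmatory, because the endpoint is major secondary, Test 2 refers to the section that holds the rule, and Table RHCF.6.4 labels the comparison that way. Another could cite the closing line of SAP 6.6 and call it unadjusted. In a head-to-head trial such a statement would be prominent, so its status should not be left to interpretation once results are known.

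The statistical issue is the branching, not the switch from noninferiority to superiority. Once Tests 1 and 2 succeed, ACR50 superiority and PASI 100 superiority are both open, each at its full level, and neither gates the other. A fixed sequence controls error only along a single ordered line.

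**Working it through.** **Inputs** (SAP 5.2): 275 per arm; ACR50 43.8% on ixekizumab and 44.1% on adalimumab; PASI 100 46.9% and 23.7%; composite 31.3% and 13.6%; margin -12 points, one-sided 0.025.

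**The plan's own figure.** Noninferiority power is Phi((0.12 - 0.003)/SE - 1.96), with SE = sqrt(0.441 x 0.559/275 + 0.438 x 0.562/275) = 0.0423. This gives Phi(0.804) = 78.9%, against the stated 78%: reproduced. At the same rates the chance that the lower limit exceeds zero is Phi(-0.003/0.0423 - 1.96) = 2.1%, so the plan does not expect to make this claim.

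**Bound on the error.** After Tests 1 and 2, a false ACR50 superiority claim has a 2.5% chance (one direction) and a false PASI 100 claim 5% (two-sided). The sum is 7.5%; under independence, 1 - 0.975 x 0.95 = 7.4%.

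**Correlations implied by the planning rates** (composite minus product of marginals, over the product of the standard deviations):

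- ixekizumab: (0.313 - 0.438 x 0.469)/sqrt(0.438 x 0.562 x 0.469 x 0.531) = 0.43
- adalimumab: (0.136 - 0.441 x 0.237)/sqrt(0.441 x 0.559 x 0.237 x 0.763) = 0.15

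**Simulation.** 1,000,000 trials per case, 275 per arm, with the four joint ACR50/PASI 100 outcomes drawn as a multinomial. The primary test (favouring ixekizumab) and the PASI 100 test used a pooled z-test in place of the logistic model. ACR50 noninferiority and superiority used the simple asymptotic interval of SAP 6.7. The equal rates below (ACR50 44% in both arms, and a range for PASI 100) are assumptions.

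| Case | Any false superiority claim, as written | Listed tests only, or ACR50 superiority placed last |
|---|---|---|
| PASI 100 as planned (46.9% vs 23.7%), ACR50 equal | 2.67% (ACR50 only) | 2.67% if ACR50 is placed last |
| Both equal, correlations 0.43 and 0.15, PASI 100 at 23.7 / 30 / 35 / 40 / 46.9% | 4.53 / 4.63 / 4.65 / 4.70 / 4.95% | 2.37 / 2.39 / 2.38 / 2.37 / 2.59% |
| Constructed: both equal, composite held at 31.3% vs 13.6%, PASI 100 at 35 / 40 / 46.9% | 6.26 / 6.45 / 6.93% | 3.84 / 4.01 / 4.43% |

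PASI 100 is counted two-sided in the last two rows. Counting only claims that favour ixekizumab, the constructed case gives 4.8 to 4.9%, against 2.3 to 2.4%. To keep the composite apart while both marginals are equal, that case needs ACR50/PASI 100 correlations of 0.67 / 0.56 / 0.43 on ixekizumab and -0.08 / -0.16 / -0.28 on adalimumab. Independent repeats agreed within simulation error; the lowest figure for the constructed case was 6.2%.

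The two descriptions of the last column coincide in rows two and three. If ACR50 superiority is tested only after PASI 100 has succeeded, a false ACR50 claim there can only follow a false PASI 100 claim, so it adds no trials with an error.

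**Power of the ordered version.** With ACR50 truly 53% vs 44% and PASI 100 as planned, ACR50 superiority is declared in 57.65% of trials in either order.

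**The case against.** The strongest reply is that the plan already answers the question. ACR50 superiority is not listed, the closing line of SAP 6.6 says unlisted analyses are unadjusted, and the stated ACR50 objective is noninferiority. On a strict reading that is right, and it is why this is a minor point. It does not remove the conflicting signals in SAP 6.12.1.2 and Table RHCF.6.4, or the flat declaration in SAP 6.7.

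Second, testing superiority after noninferiority on one interval needs no alpha adjustment. That stands for one endpoint alone. It does not cover a second endpoint opened by the same gate.

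Third, exceeding 5% takes an artificial configuration: identical marginals, opposite-sign correlations in the two arms, and counting claims that adalimumab is better on PASI 100 after ixekizumab has won the composite. The planning rates imply positive correlation in both arms. This stands as to size. Strong control, however, is a statement about every configuration.

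A reader might also infer that SAP 6.7 is wrong to refer to the p-value where Protocol 10.3.3.3 relies on the interval, and that the interval should decide. The documents do not support that. SAP 6.2.1 makes the stratification-adjusted logistic model the primary method for binary endpoints, SAP 6.6 tests with the primary method, and Protocol 10.3.1 allows documented changes of method in the SAP. The choice has almost no effect on the error rate, because the interval condition comes first. Only the grammar of the sentence needs repair.

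**Conclusion.** The point holds as a minor one. The ACR50 superiority declaration is outside the sequence and unadjusted, and strong 2-sided 5% control does not extend to it, because it runs in parallel with PASI 100 superiority.

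A reader might infer that the trial's confirmatory error control is broken, or that the primary or PASI 100 result is compromised. The documents do not support that: Tests 1 to 3 form an intact fixed sequence, and nothing in SAP 6.7 changes them. Nor is there inflation where the plan expects to be. At the planned PASI 100 rates the only possible false claim is ACR50 superiority, at about 2.7% in either order. With both endpoints equal at plan-implied correlations, the figure roughly doubles from the listed tests' 2.4 to 2.6% but stays below 5%. Only the constructed case goes above 5%.

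These sizes rest on the assumed equal rates, on correlations derived from the planning figures, and on z-tests standing in for the logistic model. The structural conclusion does not depend on them.

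**What to change.** Preferred: add ACR50 superiority to SAP 6.6 as Test 4, tested only if PASI 100 superiority succeeds. This brings it inside the 5% control, with no measurable power cost at the planned rates.

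Failing that: state in SAP 6.7 that ACR50 superiority is supportive and outside the family-wise control.

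With either choice, make the Table RHCF.6.4 label for the ACR50 Week 24 logistic comparison agree with it, and repair the grammar of the SAP 6.7 sentence without changing which statistic decides.

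The cost is a sentence and a table label in the SAP, with no extra patients and no change to the sample size or the listed tests. Protocol 10.3.1 allows such changes to be documented, with their justification, in the SAP and/or the study report, so a protocol edit is not required. It sets no deadline before the Week 24 lock, though settling the status before that lock is sensible.

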5.3. Method of Assignment to Treatment

Patients who meet all Visit 1 and Visit 2 eligibility criteria for enrollment will be randomized at Visit 2 (Week 0) in a 1:1 ratio to open-label treatment with ixekizumab or adalimumab at Week 0 (Visit 2). Assignment to treatment groups will be determined by a computer-generated random sequence using an interactive web-response system (IWRS). The IWRS will be used to assign investigational product to each patient. Site personnel will confirm that they have located the correct investigational product by entering a confirmation number found on the investigational product into the IWRS. The randomization will be stratified by concomitant csDMARD use at baseline (Yes, No) and moderate-to-severe plaque psoriasis involvement (Yes, No).

6. A Priori Statistical Methods

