6.2. Analysis Methods

6.2.1. Categorical

Unless specified otherwise, the primary analysis method for the binary categorical efficacy and health outcome variables will be a logistic regression model with treatment, concomitant csDMARD use at baseline, and moderate-to-severe plaque psoriasis involvement as factors. The odds ratios and the corresponding 95% CIs will be reported. Fisher's exact test will be used as the secondary analysis method.

For ordinal categorical variables, a logistic regression model using cumulative logits will be used.

Treatment differences (Absolute Risk Reductions [ARR]), Relative Risks (RR), Numbers Needed to Treat (NNT) estimates, and their corresponding 95% CIs (using normal approximation) will also be reported. See [Appendix 1](#) for more details.

The statistical methodology for assessing noninferiority of ixekizumab to adalimumab for ACR50 is described in [Section 6.7](#).

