6.3. Adjustments for Covariates

The randomization at the beginning of Open-Label Treatment Period (Period 2) is stratified by concomitant csDMARD use at baseline (Yes, No) and moderate-to-severe plaque psoriasis involvement (Yes, No). Unless otherwise specified, all efficacy and health outcome analyses during Period 2 will include the concomitant csDMARD use at baseline and moderate-to-severe plaque psoriasis involvement in the model. In general, when an MMRM is to be used for analyses, baseline value and baseline-by-visit interactions will be included as covariates; when an ANCOVA is to be used for analyses, baseline value will be included as a covariate.

The OBSMARGINS/OM option will be used in the LSMEANS statement in SAS to account for imbalance in the stratification variables.

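### Should the ACR50 noninferiority interval be stratified because randomisation is?

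*SAP*

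**What the plan says.** SAP Section 5.3 and Protocol Section 7.2 stratify the 1:1 randomisation by two yes/no factors, csDMARD use at baseline and moderate-to-severe plaque psoriasis. This gives four strata. For binary endpoints, SAP Section 6.2.1 makes the main analysis a "logistic regression model with treatment, concomitant csDMARD use at baseline, and moderate-to-severe plaque psoriasis involvement as factors". Section 6.6 sends the primary endpoint (Test 1) and PASI 100 (Test 3) to that model.

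Test 2, ACR50 noninferiority, follows another route. Section 6.2.1 says: "The statistical methodology for assessing noninferiority of ixekizumab to adalimumab for ACR50 is described in" Section 6.7. Section 6.6 says that if Test 1 succeeds, "then a noninferiority test for the major secondary endpoint #1 will be performed using the methods described in Section 6.7". Section 6.12.1.2 repeats the assignment. Section 6.7 compares the lower limit of a 2-sided 95% interval for the difference in response rates with -12.0 points, and it fixes the interval: "The 95% CIs for the difference in proportions will be calculated using the simple asymptotic method, without continuity correction". Protocol Section 10.3.3.3 has the same rule, with the interval "calculated using the simple asymptotic method, without continuity correction".

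The general covariate rule in SAP Section 6.3 opens with an exception clause: "Unless otherwise specified, all efficacy and health outcome analyses during Period 2 will include the concomitant csDMARD use at baseline" and the psoriasis factor.

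**The concern.** The usual advice is to analyse as you randomise. If the stratification factors predict ACR50, balancing them removes chance imbalance from the estimated difference. A crude variance formula still counts the between-stratum variation, so the interval is wider than it needs to be.

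Two features make this look important here. Test 2 has 78% stated power, against about 99% for each of the other two confirmatory tests (SAP Section 5.2). A failure on Test 2 also stops PASI 100 from being tested. Leaving the strata out of this test alone looks like precision lost where it is scarcest. It also looks inconsistent with Tests 1 and 3.

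**Working it through.** **1. Is the exception coherent?** Tests 1 and 3 are superiority tests, and a null of no effect can be tested on the odds-ratio scale. Test 2 has an absolute margin of -12 percentage points. An odds ratio cannot be compared with that margin, so Test 2 needs an interval for a risk difference. Section 6.2.1 treats risk differences the same way for all binary endpoints: they are given with relative risks and numbers needed to treat, and "their corresponding 95% CIs (using normal approximation) will also be reported". ACR50 is not singled out.

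**2. The plan's own power figure.** Inputs from SAP Sections 5.2 and 6.7: 275 per arm, rates 43.8% (ixekizumab) and 44.1% (adalimumab), margin 12 points, one-sided 0.025.

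- SE = sqrt[(0.441 × 0.559 + 0.438 × 0.562)/275] = sqrt(0.492675/275) = 0.04233
- Power = Φ[(0.120 - 0.003)/0.04233 - 1.960] = Φ(0.804) = 78.9%

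This agrees with the stated 78%. Exact enumeration of the Wald rule gives 79.7%.

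**3. Type I error of the planned rule.** Exact enumeration at the margin (32.1% against 44.1%) gives 2.42% one-sided, below the nominal 2.5%. If the strata predict ACR50, the planned rule becomes more conservative: about 1.9% to 2.1% at 20 points per factor on both factors, with a constant difference.

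**4. What stratification could gain.** The documents give neither stratum shares nor ACR50 rates by stratum, so these are assumed: csDMARD use 50% to 70%, moderate-to-severe psoriasis 20% to 50%, and additive effects of 0 to 20 points of ACR50 per factor. With effects d1, d2 and shares c, s, the removable variance per arm is d1²·c(1-c) + d2²·s(1-s). The most favourable constant-difference case is 20 points on both factors with 50%/50% shares:

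- removable variance = 0.04 × 0.25 + 0.04 × 0.25 = 0.02 per arm
- stratified SE = sqrt[(0.492675 - 0.04)/275] = 0.04057
- variance reduction = 0.04/0.492675 = 8.1%

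Reaching 90% power would need an SE of 0.117/(1.960 + 1.282) = 0.0361. The variance ratio is (0.0361/0.0423)² ≈ 0.727, a 27% reduction. Stratification cannot supply that.

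**5. In whole patients.** With equal arms in each stratum, the Mantel-Haenszel and crude differences are the same number, and only the SE differs. Noninferiority then needs a responder deficit below 275 × (0.12 - 1.96 × SE):

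| Interval (50%/50% shares) | SE | Limit on deficit | Largest whole deficit |
|---|---|---|---|
| Crude | 0.04233 | 10.2 | 10 |
| Stratified, 10 points per factor | 0.04189 | 10.4 | 10 |
| Stratified, 20 points per factor | 0.04057 | 11.1 | 11 |

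The SE is taken at the planning rates, so these limits are approximate. At 10 points per factor the decision is essentially unchanged. At 20 points it moves by one responder.

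**6. Simulation.** Settings: 200,000 trials per scenario, assumed blocks of 4, constant difference of -0.3 points, crude rule against Mantel-Haenszel with Sato variance, equal effect on both factors, three combinations of shares.

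| Effect per factor | Crude power | Stratified power | Change (points) |
|---|---|---|---|
| 0 points | 79.6%–79.7% | 79.4%–79.5% | -0.2 |
| 5 points | 79.7% | 79.5%–79.6% | -0.1 |
| 10 points | 79.8%–80.0% | 79.8%–80.1% | about +0.1 |
| 15 points | 80.0%–80.3% | 80.4%–80.9% | +0.4 to +0.6 |
| 20 points | 80.4%–80.6% | 81.6%–82.3% | +1.2 to +1.7 |

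If only one factor matters, the change is -0.1 to 0.0 at 10 points and +0.2 to +0.5 at 20 points. If the treatment difference also varies by 10 or 20 points between psoriasis strata, the range widens to about -0.5 to +2.8. Gains above 1 point again appear only at 20 points per factor.

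**The case for a change.** The best case for changing the plan is this. The factors were presumably chosen because they were thought to matter. Stratifying the interval needs no new data. With the Sato variance, the one-sided error stays at 2.4% to 2.5%. In the weakest link of the testing sequence, even 1 or 2 points of power is worth having. Had the method been chosen afresh at the design stage, a Mantel-Haenszel interval would have been a reasonable choice.

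That does not make the present choice a fault. No passage supports 20-point ACR50 differences on both factors, and at 0 to 5 points per factor stratification loses slightly. The result also depends on the variance estimator: a plug-in within-stratum variance gives about 2.5% to 2.7% one-sided error. Where the stratified interval does gain, it does so by making a gatekeeping rule easier to pass. Changing that rule in an open-label trial without a data monitoring committee has its own cost, and Protocol Section 10.3.1 requires any such change to be justified and documented.

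Two smaller points are true but change nothing. Table RHCF.6.4 labels the ACR50 logistic regression at Week 24 as the major secondary analysis and has no row for the noninferiority interval. This is a clerical cross-reference, because Sections 6.2.1, 6.6 and 6.12.1.2 all make Section 6.7 decisive. An ACR50 superiority statement could also pair a crude interval with an adjusted p-value. Section 6.7 bases that statement on the p-value, and it lies outside the testing sequence.

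**Conclusion.** The concern does not hold. The unstratified interval is a deliberate, prespecified and valid choice. Protocol and SAP agree on it, the covariate rule permits it, and it protects the type I error. The precision forgone is near zero unless both factors predict ACR50 strongly. With a constant treatment difference, the change in power runs from about -0.2 to +1.7 points over the assumed grid. With a difference that varies between psoriasis strata, it runs from about -0.5 to +2.8 points. These figures rest on assumed stratum shares, effects and block size. The conclusion does not, because the crude test is valid whatever those values are. The modest planned power is a feature of sample size and margin, and stratifying the interval would not cure it. Following the plan as written gives a sound noninferiority conclusion.
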